#### Criteria for exclusion:

None

**Sample size:** For aim 1 and 3, a Monte Carlo-based power estimate was derived using Mplus with 10,000 replications. For the sample size of 180, assuming a Type I error rate of 5%, a two-tailed test, statistical power was .83 to detect a medium-sized effect (r = .30) of randomization group on longitudinal changes, given an expectation of a small (r = .15) effect for the control group. For aim 2, power was calculated using G\*Power. Given the brevity of the three-month follow-up questionnaire, a 10% attrition rate was assumed. Assuming a Type I error rate of 5%,

a two-tailed test, and a 25% rate of seeking EBPs in the researcher-only condition, statistical power was .82 to detect a medium effect (odd ratio = 1.72).

**Randomization:** Participants will be cluster randomized by school using restricted randomization with Excel's random number generator.

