#### **INTERVENTIONS**

**Presentation:** The outreach presentation will last 75 minutes with an additional 15 minutes for caregiver questions. The presentations will occur in the evening via Zoom. The presentation will include information about identifying anxiety disorders, strategies for caregivers to help their youth with anxiety, evidence-based practices to treat youth anxiety, and strategies for finding a therapist who uses cognitive behavior therapy with exposures. The text on the presentations is written at a 5.3 grade reading level. Presentations will incorporate stigma reduction strategies, such as education to dispel myths, and behavioral decision-making tools to elicit hope, empowerment, and motivation.

**Researcher-Only condition:** The researcher-facilitated presentation, led by two clinical psychology graduate students, will be the same for all schools.

**Key opinion leader:** The key opinion leader (KOL) co-facilitated presentations will include the same core principles as the researcher-facilitated presentation but may vary by school in terms of specific examples and content emphasized based on KOL feedback. A caregiver KOL from the local community will co-facilitate the presentation with a clinical psychology graduate researcher. To select the KOLs, the principal investigator will contact the school PTA (or a similar parent group), and PTAs will be asked, "please nominate a caregiver who is well-known and respected within your community, and who reflects the diversity of the school as a whole." The PI will meet with the KOLs to review the presentation and to engage them in championing cognitive behavior therapy for youth anxiety.

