#### Planned Analyses

**Quantitative Analyses:** All analyses will use multilevel modeling to account for the nesting of repeated measures within caregivers. Preliminary analyses will examine the effect of clustering of caregivers within schools. If schools account for more than 10% of variance in the outcomes after controlling for condition, a three-level multilevel model will be used to account for nesting of repeated measures within caregivers within schools.

Analyses will consider intention to seek CBT with exposures (Treatment Seeking Evaluation - Intention to seek CBT), subjective norms about seeking CBT (Therapy Subjective Norms Questionnaire—CBT), attitudes about CBT (Caregiver Attitudes about CBT), caregiver stigma about mental illness (Parents' Internalized Stigma of Mental Illness Scale), and knowledge about how to seek EBPs for youth anxiety (Parent Engagement in Evidence-Based Services Questionnaire—Knowledge Subscale) as person-level dependent factors; condition (caregiver or

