researcher co-facilitator) as a person-level predictor; and time (pre- and post-presentation) as an observation-level predictor. In separate multilevel models, (a) intention to seek CBT, (b) Therapy Subjective Norms Questionnaire—CBT, (c) Caregiver Attitudes about CBT, (d) Parents' Internalized Stigma of Mental Illness Scale, and (e) Parent Engagement in Evidence-Based Services Questionnaire-Knowledge subscale will be regressed on time, condition, and the interaction between time and condition; a random intercept will be included in all five multilevel models. A binary logistic regression will be conducted with CBT service seeking at the threemonth follow-up (Treatment Seeking Evaluation - Actual CBT seeking) entered as the dependent variable, condition entered as the independent variable, and youth anxiety (Brief Revised Child Anxiety and Depression Scale-Total Anxiety) entered as a control variable. Ttests will be used to compare difference between conditions for each item on the Relatability Evaluation of the principal investigator. This study will examine caregiver demographic factors, youth anxiety (Brief Revised Child Anxiety and Depression Scale-Total Anxiety), racial similarity to the presenter (Demographics, same race), and self-disclosure (Content Checklist, selfdisclosure), as potential moderators of the effect of presentation condition on intention to seek CBT. In separate multilevel models, intention to seek CBT will be regressed on time, condition, each potential moderators, and their three-way interaction.

**Qualitative Analyses:** The transcribed qualitative interviews will be entered into NVivo software for analysis. Qualitative analyses will use a direct content analysis approach (Hsieh & Shannon, 2016). The coding team will create an initial codebook using the primary topics asked in the qualitative interviews. Additional codes will be added to code text that does not fit into the initial categories, either to split the initial codes into two, or to create new codes. Coding will occur through a consensus process in which each transcript will be coded independently by two raters, who will arrive at consensus through discussion (Hill et al., 2005). Thematic responses will be examined by both condition and by whether the caregiver has sought treatment for their youth (4 groups total).

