**Integration Procedures:** Mixed methods integration will follow a QUAN → qual structure with an expansion approach (Palinkas et al., 2010); quantitative methods being used to test hypotheses about the intervention and qualitative methods being used to contextual the results.

**Data collection at the time of the SAP:** As of 8/11/21, pre/post presentation data has been collected from 17 participants. Three-month follow-up data has not yet been collected. No data has been analyzed.

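### Schools are randomised, but the tests of CBT seeking and Relatability have no school term, and the 10% rule does not protect the pre/post interaction tests

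*Combined protocol and SAP*

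**What the plan says.** The Study Design section describes a two-arm cluster randomised trial, and the Randomization paragraph under Participants says "Participants will be cluster randomized by school using restricted randomization".

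The SAP's Planned Analyses section then provides the following:

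- **General structure.** Multilevel models handle repeated measures within caregivers. School enters only on a condition: "If schools account for more than 10% of variance in the outcomes after controlling for condition, a three-level multilevel model will be used". Condition is treated as a person-level predictor.
- **Five pre/post outcomes, including intention (primary outcome 1).** Each is regressed on time, condition and their interaction, and "a random intercept will be included in all five multilevel models". No school-by-time term is mentioned.
- **CBT seeking (primary outcome 2).** "A binary logistic regression will be conducted with CBT service seeking at the threemonth follow-up". Condition is the predictor and youth anxiety the covariate; nothing else is listed.
- **Relatability (Hypothesis 3).** "Ttests will be used to compare difference between conditions for each item on the Relatability Evaluation".

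The documents give no number of schools, ICC, cluster-robust standard error or small-sample correction. The Sample size paragraph contains no design effect.

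**The concern.** When whole schools are allocated, caregivers in the same school share a presentation, a presenter pair and a community. Their outcomes may be correlated, and chance differences between schools become part of the difference between arms. A test that treats caregivers as independent then has standard errors that are too small.

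- **CBT seeking and Relatability** are each measured once per caregiver. The provision for repeated measures does not apply to them, and the three-level remedy does not fit them. Any between-school variation inflates the error rate, so a school difference can be read as a KOL effect.
- **Intention and the other pre/post outcomes** are tested through the time-by-condition interaction. A stable school difference cancels from it. Error rises only if schools differ in how much caregivers change. That is plausible, because KOL presentations "may vary by school in terms of specific examples and content emphasized based on KOL feedback". The 10% rule looks at the school share of outcome variance rather than of change, and a school intercept leaves the interaction test as it was.

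**Working it through.** **Inputs from the documents.** N = 180; 10% attrition, so 180 × 0.9 = 162 at three months (81 per arm); 25% seeking rate; two-sided 5%. **Assumed, because not stated:** k = 6 to 36 schools of equal size, ICC ρ = .01 to .10, 1:1 allocation, and a pre-post correlation of .6.

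**The plan's own figure.** The Sample size paragraph reports "a two-tailed test, and a 25% rate of seeking EBPs in the researcher-only condition, statistical power was .82" for an odds ratio of 1.72. The odds are .25/.75 × 1.72 = .573, so p = .573/1.573 = .364. With 81 per arm, two-arm power is 0.35 to 0.36. A value near .82 (0.80 to 0.85) appears only if condition is treated as a standard-normal continuous predictor. That discrepancy is a separate matter; here the point is that neither version contains a design effect. At ρ = .05 the 162 are worth about 83/100/120 independent caregivers for 8/12/20 schools. Power falls to 0.52/0.59/0.67 on the continuous-predictor basis (0.80 before clustering) and to 0.20/0.23/0.27 for two arms.

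**Step 1: approximation.** With m caregivers per school, DE = 1 + (m − 1)ρ, and the actual error is about 2[1 − Φ(1.96/√DE)].

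- CBT seeking, k = 10, ρ = .05: m = 16.2, DE = 1 + 15.2 × .05 = 1.76, error about 14.0%.
- Relatability, k = 10, ρ = .05: m = 18, DE = 1 + 17 × .05 = 1.85, error about 15.0%.

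**Step 2: simulation.** There were 20,000 null trials per cell. CBT seeking used beta-binomial schools (ICC on the proportion scale) and a logistic Wald test with a null covariate standing in for youth anxiety. Type I error at ICC .01/.02/.05/.10:

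| Schools | CBT seeking, N = 162 | Relatability t-test, N = 180 |
|---|---|---|
| 6 | 7.8/10.9/19.3/30.5% | 8.6/11.6/21.7/32.7% |
| 10 | 6.7/8.5/13.6/21.9% | 7.2/9.0/15.1/24.0% |
| 18 | 5.9/6.6/9.7/13.9% | 6.1/7.1/10.4/15.6% |
| 32 (seeking) or 36 (Relatability) | 5.2/5.4/7.0/9.6% | 5.6/5.6/7.3/10.1% |

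A t-test on school proportions held 4.6 to 5.2%.

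**Step 3: pre/post interaction.** With complete pairs, the interaction test in a random-intercept model is a t-test on change. A school effect present at both times subtracts out, and simulated error was then 4.7 to 5.3%. If instead the ICC is that of the change (N = 180, same four values):

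| Schools | Interaction test, school ignored |
|---|---|
| 6 | 8.5/12.5/21.6/33.1% |
| 10 | 6.9/9.1/15.2/23.9% |
| 18 | 5.9/7.0/10.5/15.3% |
| 36 | 5.4/5.9/7.5/9.7% |

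A t-test on school-mean changes held 4.7 to 5.3%.

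**Step 4: does the 10% rule help?** For 6/10/18/36 schools:

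- Change ICC .10 and no stable school effect: the rule is triggered in only 2.1/1.6/2.1/4.9% of trials.
- Stable ICC .10 and change ICC .10: it is triggered in 50/56/60/61%, yet interaction error among those trials is still 32/24/15/10%.

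Direct mixed-model fits show why. In 12 data sets with 10 schools, the interaction standard error agreed to four decimals in the two-level and the three-level intercept models (for example 0.1340 and 0.1340). With a school-by-time term it was 0.14 to 0.32.

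**The case against.** - **The plan may already cover CBT seeking.** Planned Analyses opens with a statement about all analyses, and the 10% rule names no exceptions. But that statement concerns repeated measures, and the same section then names a single-level logistic regression. At best the two need reconciling. Even the generous reading omits school when its share is 10% or less. With a true share of 5% in a pre/post outcome, the rule was triggered in only about 12 to 13% of simulated trials.
- **The pre/post part is conditional.** This stands. The documents give no figure for school variation in change, and the variable content is described only for the KOL arm. If change varies only there, with 10 schools and ICC .05, the average design effect is (1.85 + 1)/2 = 1.425 and error is about 10%, not 15%.
- **The three-level random effects are not spelled out.** Also fair: intercepts only is the natural reading but an inference. Left open, the rule still does not commit to a school-by-time term.
- **The ICC scale matters.** On the latent logistic scale, CBT-seeking error at ICC .05 is 14.2–14.3/10.3–10.8/8.1–8.3/6.1–6.6% for 6/10/18/32 schools, lower than tabulated. The direction is unchanged.
- **Restricted randomisation and youth anxiety could absorb school variation.** True. Pairing schools on a factor that explains half the between-school variance (an assumption; no factor is named) gives 10.7/7.9/6.3/5.8% at latent ICC .05.
- **Relatability is listed as exploratory and serves a secondary aim.** Correct. It adds little to the weight of the point.

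**Conclusion.** The concern holds, and the plan should be changed. The test of CBT seeking, a primary outcome, ignores the unit of randomisation as written; so do the Relatability t-tests. For intention, the plan's only safeguard examines the wrong variance and, with intercepts only, leaves the test unchanged.

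The direction is firm, but the size is not. It depends on the number of schools, the ICC and its scale, and any restriction used in randomising, none of which is stated. For CBT seeking, the assumed ranges run from negligible (5.2% with 32 schools, ICC .01) to severe (30.5% with 6 schools, ICC .10). At 10 schools and ICC .05, error is about 14% on the proportion scale and about 10.5% on the latent scale. The pre/post inflation arises only if schools differ in change; otherwise those tests stay near 5%.

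**What to change.** Delete the 10% trigger, treat condition as a school-level factor, and account for school in every between-condition analysis:

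- **CBT seeking:** a mixed logistic model with a school random intercept, GEE with a small-sample correction, or a comparison of school-level results. Keep youth anxiety as a covariate where the method allows.
- **Pre/post models:** a school random intercept plus a school-by-time random effect, or a comparison of school-mean changes. A school intercept alone is not enough.
- **Relatability:** a school random effect or a school-mean comparison.
- **Throughout:** degrees of freedom based on the number of schools. State that number, the assumed ICC and its scale, and the factors used in the restriction.

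**Cost.** SAP wording and slightly more modelling. Intervals widen: at ICC .05 the standard error for CBT seeking grows by √(1 + (162/k − 1) × .05) = 1.52/1.33/1.18/1.10 for 6/10/18/32 schools, so power falls. A two-sample comparison of school means has k − 2 degrees of freedom, or 4/8/16/30. If change does not differ by school, the intention analysis gives up degrees of freedom for little gain.

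**Timing.** At its stated date the SAP reports "Three-month follow-up data has not yet been collected. No data has been analyzed". Pre/post data from 17 participants were already in hand, but on that status the change could be specified without knowledge of results.

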## **Primary Aims**

**Aim 1:** Test the relative effects of researcher-only and KOL conditions on changing caregivers' intention to seek CBT for their youth, and actual CBT seeking at three-month follow up.

*Hypothesis 1a:* Relative to the researcher-only condition, the KOL condition will result in a greater increase in intention to seek CBT with exposures.

*Hypothesis 1b:* Relative to the researcher-only condition, the KOL condition will result in a greater seeking of CBT with exposures for their youth at the three-month follow-up.

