## **MEASURES**

#### Primary outcome measure:

1. Change From Pre-Presentation to Post-Presentation in Treatment Seeking Evaluation - Intention to Seek Cognitive Behavioral Therapy [Time Frame: pre-presentation; post-presentation (within 1 week after the presentation)]

Participants rate how likely they are to seek a therapist who uses exposure therapy for their child in the next three months on a scale ranging from 1 (*very unlikely*) to 5 (*very likely*).

2. Number of Participants Who Sought Cognitive Behavioral Therapy as Assessed by Treatment Seeking Evaluation - Actual Cognitive Behavioral Therapy Seeking [Time Frame: 3-month follow-up]

Participants indicate whether they sought exposure therapy for their child since the presentation (yes/no).

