#### STATISTICAL ANALYSIS PLAN:

**Missing Data:** Potential sampling biases will be identified by multiple logistic regression analyses examining whether key predictors at baseline (primary and secondary outcome measures; demographics) are associated with study retention. Should analyses reveal that dropout is differentially associated with outcomes, multiple imputation will be used.

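### Optional efficiency gain: the CBT-seeking model leaves out the pre-presentation intention rating, which could modestly raise power if that rating is prognostic

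*Combined protocol and SAP*

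**What the plan says.** In the combined protocol and SAP, Planned Analyses specifies a binary logistic regression for hypothesis 1b. Three-month CBT seeking is the outcome, condition is the predictor, and youth anxiety is the only adjustment: "youth anxiety (Brief Revised Child Anxiety and Depression Scale-Total Anxiety) entered as a control variable".

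The primary outcome measures include two items about the same behaviour. At three months, "Participants indicate whether they sought exposure therapy for their child since the presentation (yes/no". Before and after the presentation, "Participants rate how likely they are to seek a therapist who uses exposure therapy for their child in the next three months". The pre-presentation rating enters its own time-by-condition model for hypothesis 1a but not the seeking model, and no reason is given.

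The Missing Data paragraph deals with dropout: "Should analyses reveal that dropout is differentially associated with outcomes, multiple imputation will be used". It gives no rule for a caregiver who answers at three months but lacks a baseline covariate. Youth anxiety, already in the model, is also measured only before the presentation.

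The closing note on data collection records that no three-month data had been collected and nothing analysed when the SAP was written.

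**The concern.** The pre-presentation rating and the outcome concern the same behaviour, the same child and the same three months. No other listed baseline measure comes as close. The plan already accepts covariate adjustment, and eligibility sets no anxiety or treatment-need criterion, so initial intention may vary widely.

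If the rating predicts seeking, the planned model gives up some power on a primary outcome, and a chance arm difference in intention stays in the estimate. If it does not predict seeking, almost nothing is lost either way. A weak link is plausible, because the rating precedes a presentation that teaches "strategies for finding a therapist who uses cognitive behavior therapy with exposures".

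**Working it through.** **Inputs from the documents.** The Sample size paragraph gives a 25% seeking rate in the researcher-only condition, a two-sided 5% test and attrition ("Given the brevity of the three-month follow-up questionnaire, a 10% attrition rate was assumed"). It labels this calculation aim 2, but the content is CBT seeking. It states no N there; 180 is given for aims 1 and 3 and is assumed here. Analysed N = 180 × 0.9 = 162, or 81 per arm at an assumed 1:1 ratio.

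**The plan's own figure.** The paragraph says "statistical power was .82 to detect a medium effect (odd ratio = 1.72". Odds in the KOL arm = (0.25/0.75) × 1.72 = 0.573, so the rate is 0.573/1.573 = 36.4%. The difference is 0.114, with SE = √[(0.25×0.75 + 0.364×0.636)/81] = 0.072. Power ≈ Φ(0.114/0.072 − 1.96) ≈ .35 to .36. The .82 is not reproduced for a two-arm comparison. That is a separate issue; the gains below start from about .36.

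**Assumptions not in the documents.** Intention OR per SD, given anxiety, of 1.0, 1.5, 2.0 or 3.0; anxiety OR 1.5 per SD; correlation .3 between the two; intention cut to five categories. Marginal rates are held at 25% and 36.4%.

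**Step 1: power without clustering.** Each cell shows planned (condition + anxiety) → adjusted (+ intention).

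| Intention OR per SD | 1.0 | 1.5 | 2.0 | 3.0 |
|---|---|---|---|---|
| Run A (6,000 replicates) | .365→.365 | .356→.360 | .359→.384 | .380→.424 |
| Run B (8,000 replicates) | .358→.358 | .369→.375 | .364→.385 | .367→.416 |
| Run C | .355→.357 | .364→.367 | .372→.397 | .373→.422 |
| Gain, points | 0.0–0.2 | 0.3–0.6 | 2.1–2.5 | 4.4–4.9 |

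A further run gave about 0, 1, 2 and 6 points. The Monte Carlo SE of one power value at 6,000 replicates is √(.36×.64/6000) = .006, so gains below 1 point are read as about zero. With no true effect, rejection in runs A and B was .044 to .051 with or without intention.

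**Step 2: where precision improves (run A).**

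| Intention OR per SD | 1.0 | 1.5 | 2.0 | 3.0 |
|---|---|---|---|---|
| SD of standardised risk difference | .0717→.0720 | .0707→.0699 | .0694→.0671 | .0693→.0643 |
| SD of conditional log-OR | .367→.371 | .368→.377 | .367→.384 | .369→.410 |
| Mean conditional log-OR | .581→.585 | .578→.596 | .593→.642 | .606→.720 |

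The conditional log-OR becomes less precise, but its mean moves further from zero. At intention OR 3.0 the ratio of mean to SD goes from .606/.369 = 1.64 to .720/.410 = 1.76, which is where the power comes from. The risk difference does become more precise: at 3.0 its SD falls by 1 − .0643/.0693 = 7%.

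**Step 3: power with clustering.** The number of schools and the intraclass correlations (ICCs) are not given; the values below are assumed. The test is a school-level t-test on residuals, which is neither the planned nor the proposed model. There were 4,000 runs per cell, and restricted randomisation was not modelled.

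| Schools; ICC seeking/intention | 1.0 | 1.5 | 2.0 | 3.0 |
|---|---|---|---|---|
| 6; .02/.02 | .196→.194 | .204→.210 | .196→.200 | .209→.236 |
| 6; .05/.10 | .139→.134 | .151→.151 | .149→.160 | .158→.181 |
| 18; .02/.02 | .303→.301 | .315→.318 | .316→.329 | .317→.365 |
| 18; .05/.10 | .272→.269 | .269→.266 | .270→.295 | .288→.350 |

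Gains are −0.5 to 0.6 points at OR 1.0 to 1.5, 0.4 to 2.5 at 2.0 and 2.3 to 6.2 at 3.0.

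**Step 4: missing ratings.** With 10% of intention ratings missing at random and no clustering (5,000 runs), power at intention OR 1.0/1.5/2.0/3.0 is:
- as planned: .360/.357/.373/.359
- adjusted, those caregivers dropped: .323/.340/.361/.386
- adjusted, filled with the mean over both arms: .359/.364/.394/.412

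Dropping cases costs 1 to 4 points up to OR 2.0; filling avoids that. Only the intention item was missing in these runs.

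**Step 5: chance imbalance, no true effect.** If intention differs by 0.25 SD between arms, the planned model gives OR 1.00/1.11/1.17/1.27 and the adjusted model 1.00/1.01/1.01/1.03. This is the same efficiency gain seen for one unlucky allocation. It is not bias.

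**The case against.** The strongest reply is that this is analyst's choice. The plan prespecifies the outcome, the condition term and one sensible covariate, and the benefit of another rests on a prognostic strength the documents do not give. At OR 1.5 per SD the gain is negligible, and only OR 3.0, which nothing in the documents supports, gives more than about 3 points. All of that stands, and it is why the point is optional.

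Two further objections also stand. The planned effect measure is an OR, and its standard error rises with adjustment, so the precision gain is confined to a marginal measure that the plan does not yet contain. A rule for missing intention alone would not keep every caregiver with a follow-up answer, because the anxiety score can be missing too. A caregiver who skipped the whole pre-presentation assessment lacks both and is lost under the planned model as well. The rule must therefore cover both covariates.

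A reader might infer that leaving out intention biases the hypothesis 1b comparison or invalidates the test. The documents do not support that. Condition is randomised, chance imbalance is part of the ordinary sampling error, and rejection under no effect stayed near 5% in the unclustered runs with or without the covariate.

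**Conclusion.** The point holds as an optional efficiency improvement. Under the assumed 25% control rate, OR 1.72 and 162 caregivers, it is worth about 0 power points at an intention OR of 1.0 to 1.5 per SD, 1 to 3 at 2.0 and 4 to 6 at 3.0 without clustering, and similar or smaller amounts with it. If the rating is not prognostic, the simulated loss is at most about half a point.

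These sizes rest on assumed values for prognostic strength, the anxiety effect, the correlation, the number of schools and the ICCs. Adjustment offsets imbalance in this rating only, not in other caregiver factors or between schools.

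It would also be wrong to infer that the covariate repairs the power or the clustering of this analysis. Power stays far below .82. In the clustered settings, the individual-level logistic model rejects a true null in .056 to .150 of runs as planned and .057 to .149 adjusted. Both are separate issues that this change leaves untouched.

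**What to change.** In the Planned Analyses sentence on CBT seeking:

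- Enter pre-presentation intention to seek CBT (1 to 5) beside youth anxiety as a control variable.
- State that post-presentation intention is not entered, because hypothesis 1a expects condition to change it: "the KOL condition will result in a greater increase in intention to seek CBT with exposures".
- Add a rule for missing covariates: if pre-presentation intention or youth anxiety is missing, replace it by its mean over both conditions, or include it in the multiple imputation if that is run, so that no caregiver with a follow-up answer is dropped for a missing covariate.
- Report the standardised marginal risk difference beside the conditional OR, with a standard error consistent with however school clustering is handled.

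The cost is a few sentences and no new data. With no three-month data collected at the SAP date, the change could be prespecified then. If outcomes have since been seen by condition, it should be labelled as added later.

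The downside is interpretation: the OR becomes conditional on intention as well as anxiety. Under the assumptions above, a marginal OR of 1.72 corresponds to about 1.75 given anxiety alone (intention not prognostic), and to about 1.80, 1.87 and 2.0 given both covariates at intention OR 1.5, 2.0 and 3.0. The marginal risk difference keeps the result readable.

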## **Secondary Aims**

**Aim 2:** Test the relative effects of researcher-only and KOL conditions on changing caregivers' (a) perceived subjective norms about seeking CBT, (b) attitudes about CBT, (c) stigma about mental illness, and (d) knowledge of how to seek EBPs.

*Hypothesis 2a:* Relative to the researcher-only condition, the KOL condition will result in a greater (a) increase in subjective norms about seeking CBT, (b) attitudes about CBT, and (c) decrease in caregiver stigma about mental illness.

*Hypothesis 2b:* Both presentation conditions will result in a similar increase in knowledge about how to seek EBPs.

**Aim 3:** Examine how KOLs affect participants' impression of the researcher presenter. **Hypothesis 3:** Participants will view the principal investigator (i.e., the first author) more favorably when she presents with the KOL, relative to when she presents with another researcher.

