### **Exploratory outcome measures:**

- 7. Change From Pre-Presentation to Post-Presentation in Barriers to Seeking Treatment [Time Frame: pre-presentation; post-presentation (within 1 week after the presentation)]

  The Barriers to Seeking Treatment questionnaire asks participants to indicate whether they agree with 21 potential barriers to treatment (Heeringa et al., 2004). A count of the total number of barriers will be used in analyses.
- 8. Change From Pre-Presentation to 3-Month Follow-Up in Barriers to Seeking Treatment [Time Frame: pre-presentation; 3-month follow-up]

The Barriers to Seeking Treatment questionnaire asks participants to indicate whether they agree with 21 potential barriers to treatment (yes/no; Heeringa et al., 2004). A count of the total number of barriers will be used in analyses.

9. Client Satisfaction Questionnaire [Time Frame: post-presentation (within 1 week after the presentation)]

The Client Satisfaction Questionnaire assesses participants' satisfaction with the presentation. Items are rated on scale ranging from 1 to 4. Items are summed; higher composite scores indicate greater program satisfaction.

10. Relatability Evaluation [Time Frame: post-presentation (within 1 week after the presentation)]

The Relatability Evaluation will be used to evaluate participants' impression of the presenter. Participants will rate each presenter (scale ranging from 1 to 5) on 10 items associated with aspects of key opinion leaders: relatable, likeable, similar, think similarly, similar beliefs, credible, trustworthy, understanding of the local community, familiar, and friendship. Items are summed; higher composite scores indicate that the presenter is more relatable.

11. Brief Revised Child Anxiety and Depression Scale-Parent Version [Time Frame: prepresentation]

The total anxiety scale (15 items) from the Brief Revised Child Anxiety and Depression Scale-Parent Version will be used to assess youth anxiety (Ebesutani et al., 2017). Participants rate items on a scale from 0 (*never*) to 3 (*always*). Items are summed; higher scores indicate higher levels of anxiety.

12. Demographics [Time Frame: pre-presentation]

A demographics questionnaire will assess caregiver and youth age, gender, race, ethnicity, and nativity; caregiver level of education, income, and religion; and youth health insurance status.

13. Content Checklist [Time Frame: during the 1.5 hour presentation]

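### Hypothesis 3 is tested by ten separate item t-tests that ignore the randomized schools, while the summed score the plan defines is never tested

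*Combined protocol and SAP*

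**What the plan says.** - **Hypothesis.** Under Secondary Aims, Hypothesis 3 states that participants will "view the principal investigator (i.e., the first author) more favorably when she presents with the KOL" than when she presents with another researcher. It is one claim with one direction.
- **Measure.** Item 10 under Exploratory outcome measures is the Relatability Evaluation: ten attributes rated 1 to 5 for each presenter, collected once, after the presentation. Its scoring rule is: "Items are summed; higher composite scores indicate that the presenter is more relatable".
- **Test.** Planned Analyses names one quantitative analysis for this aim: "Ttests will be used to compare difference between conditions for each item on the Relatability Evaluation of the principal investigator". It does not mention the sum, a key item, a multiplicity adjustment or a school term.
- **Design.** The Randomization paragraph says: "Participants will be cluster randomized by school using restricted randomization".
- **General modelling rule.** Planned Analyses opens with "All analyses will use multilevel modeling to account for the nesting of repeated measures within caregivers". It then promises a preliminary look at clustering by school. If schools explain more than 10% of outcome variance after controlling for condition, "a three-level multilevel model will be used to account for nesting of repeated measures within caregivers within schools".

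**The concern.** Three gaps meet in one sentence of the plan.

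1. An independent-samples t-test treats caregivers from one school as independent. Condition is assigned to whole schools, so any resemblance between caregivers within a school enters the comparison of arms and the test does not count it.
2. Ten tests address one hypothesis without adjustment and without a rule for combining them. The same ten p-values could be reported as supporting Hypothesis 3 or as failing to support it.
3. The score that matches the hypothesis, the sum, is defined and then left unused.

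At stake is a false claim that a key opinion leader improves how the researcher is seen. The general modelling rule looks as if it might cover this, but it is written for repeated measures and this instrument has only one measurement.

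**Working it through.** **The plan's own figure.** The Sample size paragraph gives power .83 at N = 180 for aims 1 and 3. It concerns longitudinal change, and the Mplus model and its inputs are not given, so it cannot be reproduced. It also does not describe a measure taken once. Nothing below relies on it.

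**Inputs.** From the documents: ten items, one measurement, schools randomized, two-sided 5%, N = 180. Assumed, because the documents do not give them: ICC .01, .05 or .10; m = 8, 15 or 30 caregivers per school, in equal-sized schools; equal arms; item correlation .3, .5 or .7.

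**Step 1: one t-test without a school term.** Design effect DE = 1 + (m − 1) × ICC. Actual two-sided error = 2 × P(Z > 1.96/√DE). Example: m = 15, ICC .05 gives DE = 1 + 14 × .05 = 1.70; 1.96/√1.70 = 1.503; error = 13.3%.

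| m | ICC .01 | ICC .05 | ICC .10 |
|---|---|---|---|
| 8 | 5.8% | 9.2% | 13.3% |
| 15 | 6.6% | 13.3% | 20.6% |
| 30 | 8.4% | 21% | 32% |

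**Step 2: ten items, no combining rule.** This used 1,000,000 draws of ten equally correlated z-statistics, scaled by √DE. An item counts if it exceeds 1.96 in the hypothesized direction (nominal 2.5%). At item correlation .5:

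| Items required | No clustering | m = 15, ICC .05 |
|---|---|---|
| at least 1 | 14% | 30% |
| at least 2 | 5.5% | 15% |
| at least 3 | 2.6% | 8.8% |
| at least 5 | 0.7% | 3.1% |

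With the same clustering, the chance of at least one false item is 38% at correlation .3 and 23% at .7. Simulating caregivers directly (12 schools of 15, ICC .05, correlation .5) gave 13.5% per item and 31% for at least one item, which agrees.

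**Step 3: is the sum alone enough?** No. In that simulation a t-test of the sum that ignores school had 13.5% error. If the school effect is fully shared across items, this rises to about 19%. A test of the sum on school means (10 df) had 5.0%.

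**Step 4: would the 10% rule repair it?** ICCs of .01 and .05 lie below the trigger, so a school level would usually be left out. Step 1 shows 9% to 21% error per item at ICC .05.

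**The case against.** The strongest reply is that this is loose drafting in a low-stakes place. The instrument is listed as exploratory, its ten attributes differ in content, and item-by-item description is defensible. The t-test sentence can be read as a specific exception for an outcome measured once, as the logistic regression for three-month seeking is an exception to the general rule. That regression also names no school term, so the omission is not peculiar to Hypothesis 3. The promised preliminary look at clustering is worded generally and could include this outcome.

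Much of this stands, and it limits the priority. It does not remove the problem. The t-tests are the only quantitative test of a numbered hypothesis under a secondary aim, and a preliminary look does not put a school term into the test.

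A reader might go further in three ways that the documents do not support.

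- *That the general modelling rule contradicts the whole t-test plan.* It differs only on the type of model and, above 10% school variance, on a school level. It says nothing about the sum or a decision rule. Reconciling the two statements is needed, but would not by itself cure the error.
- *That 30%, or any other single figure, is the plan's error rate.* The rate depends on an unstated counting rule and on assumed ICC, school size and item correlation. A strict rule could make it small: requiring six items gives 1.8% at ICC .05, m = 15 and correlation .5. The same rule gives 3.8% at ICC .10, and 3.4% at ICC .05 with correlation .7.
- *That the stated .83 power is wrong for Aim 3.* It describes a different kind of test, so it neither supports nor refutes the power of this one.

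**Conclusion.** The concern holds in a limited form. As written, the test of Hypothesis 3 ignores the unit of randomization, does not use the score that expresses the hypothesis, and has no rule linking ten results to one claim. The direction of the clustering error needs no assumed value: any positive school ICC makes the standard error too small. Its size rests on the assumed ranges: about 6% to 8% per item at ICC .01, 9% to 21% at .05 and 13% to 32% at .10, for 8 to 30 caregivers per school. Multiplicity adds to this separately; even without clustering, at least one false favourable item is expected in about 14% of null trials at item correlation .5. The change should be made, with modest priority.

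**What to change.** State one decision rule for Hypothesis 3 and bring the t-test sentence into line with the opening of Planned Analyses.

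- **Test.** Analyse the summed Relatability score for the principal investigator once, in a linear mixed model with condition, a school random intercept and small-sample degrees of freedom. Keep the intercept whatever school variance is observed.
- **Items.** Report the ten items descriptively with school-adjusted intervals. If item-level claims are wanted, take Holm-adjusted tests from the same model and say beforehand how they bear on Hypothesis 3.

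**Cost.** SAP wording and one model on data the plan already collects. The section on data collection reports pre/post data from 17 participants so far and says "No data has been analyzed", so the rule can still be set free of results.

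Power will be lower than an unadjusted test suggests. Assume 12 schools of 15, item correlation .5 and a 0.3 SD shift in all ten items. The sum has variance 10 + 90 × .5 = 55, so d = 3/√55 = .405. At ICC .05, SE = √[2 × (.05 + .95/15)/6] = .194. The noncentrality is .405/.194 ≈ 2.08 on 10 df, and power is about 47% (63% at ICC .01, 35% at .10).

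If the school effect is fully shared across items at item ICC .05, the sum has school variance 100 × .05 = 5 and caregiver variance .95 × 55 = 52.25. Its ICC is then 5/57.25 = .087 and power is about 36%.

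Effects confined to a few items are diluted: with three of ten items shifted, composite power is about 9% at ICC .05. Item tests are no easy substitute. One shifted item has about 29% power at the 5% level and 6% at Holm's first step (.05/10 = .005).
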